3.0 THERAPEUTIC/DIAGNOSTIC AGENTS

Before any study procedures are performed (which includes all screening procedures, pre-treatment, treatment/intervention procedures, etc.), all patients will be asked to sign an informed consent form.

3.1 Imaging

After the informed consent is signed, the patient will be scheduled for an MRI (dynamic contrast enhanced and diffusion weighted imaging using a 1.5 Tesla endorectal MRI. The regions where both imaging sets indicate the potential for disease will be identified and categorized to one or more of 4 possible regions of the prostate as defined below.

3.2 Mapping Prostate Biopsy

Transrectal ultrasound-guided prostate biopsies will be performed to determine study eligibility as well as to assess treatment efficacy. The two biopsy sessions (one pre-treatment and the other 6 months after focal RFA) will follow the same method. The rational for a complete mapping biopsy after RFA, rather than just sampling of the regions that were treated, is to identify cancer lesions not found in initial MRI/biopsy (thus, not treated) or cancer that may have developed after RF treatment.

Preparation/anesthesia: The patient will be given a Fleet enema prior to the procedure and administered prophylactic antibiotics. With the patient in the lithotomy position and under general anesthesia, transperineal saturation biopsies are obtained and separated in four sections: RIGHT CENTRAL, RIGHT PERIPHERAL, LEFT CENTRAL and LEFT PERIPHERAL.

3.3 Focal RFA of the Prostate

The equipment for whole-gland RFA of the prostate is FDA cleared for clinically localized prostate cancer, and the focal RFA equipment is also commercially available. The focal RFA equipment used in this study is cleared for radiofrequency soft tissue ablation by the FDA.

Description of procedure use for the Focal RFA of the Prostate:

The patient is given a Fleets enema prior to the procedure and administered prophylactic antibiotics. The procedure is performed on an outpatient basis under general. With the patient in the lithotomy position a Foley catheter is inserted into the bladder and the scrotum is elevated toward the abdomen either by taping or with a rolled towel. Perineal shave is optional. The rectum is irrigated with normal saline to ensure adequate bowel preparation. The perineum is prepared steriley.

The bipolar RFA procedure is performed under transrectal ultrasound guidance. Transrectal ultrasound probe is inserted into the rectum. The probe is then connected to a stepper stabilizer and the pelvis is visualized at 5mm stepping increments so that the

prostate, urethra, bladder, seminal vesicles, and anterior rectal wall can all be appropriately visualized. The ultrasound images and probe driving mechanism template are mated to allow accurate position of the probe so as to precisely target the regions of the prostate that were mapped during the biopsy. The desired target will be defined by which of the previously defined four regions of the prostate had positive biopsies as described above. An appropriate insertion location of the bipolar RFA probes are designed in the planning process to target the regions of the prostate to be ablated (the number of probes will depend upon the size/shape of the prostate and the location of the lesions to be ablated).

Designated regions of the prostate will be ablated via the ENCAGE™ (Trod Medical® Bradenton, FL) RFA system. ENCAGE™ has FDA clearance for percutaneous RF soft tissue / tumor ablation. The system consists of percutaneous probes connected to a RF bipolar generator which precisely controls the ablation. Once the target areas for ablation have been identified on TRUS the ENCAGE™ RFA probe will be inserted percutaneously through the skin of the perineum into the prostate under ultrasound guidance. Once the probe is positioned containing the prostate region designated for ablation, ablation will be initiated. RFA will occur at 0.5 cm increments along the longitudinal axis of the prostate under ultrasound guidance initiating cranially towards the prostate base and moving caudally towards the apex. The number of probes inserted percutaneously into the prostate will be predefined based on the target size and shape. Only one probe will be inserted at any time with prior probes removed before inserting the next. Once ablation has been completed the prostate and bladder neck will be surveyed with the TRUS. The TRUS probe will then be removed from the rectum and the Foley catheter will be deflated and removed from the bladder.

3.4 Assessment of Quality-of-Life

Assessment of quality of life (via completion of the questionnaires) will correlate with AUA symptom score, RAS, IIEF-15, and EPIC QOL.

Medical Resource Utilization

Medical resource utilization (MRU) will be recorded weekly through patient self-report using a patient MRU diary. These MRU data will allow for a health economic evaluation of the ENCAGE™ technology.

4.0 CRITERIA FOR SUBJECT ELIGIBILITY

4.1 Subject Inclusion Criteria

Subject Population:

- Men 18 years of age or older
- Diagnosis of adenocarcinoma of the prostate, confirmed by H.L. Moffitt Cancer Center review
- No prior treatment for prostate cancer
- ECOG performance status of 0 or 1
- Prostate Cancer Clinical Stage T2a and below

- PSA <10 ng/ml (this will be the PSA level prompting the initial prostate biopsy)
- Prostate size <60 cc on transrectal ultrasound

Pre-enrollment biopsy parameters (as per H.L. Moffitt C.C. review)

- Minimum of 10 biopsy cores
- Gleason score 6 or 7
- Unilateral cancer (only right-sided or left-sided, not bilateral)

4.2 Subject Exclusion Criteria

- Men less than 18 years of age
- Medically unfit for anesthesia
- Histology other than adenocarcinoma
- Biopsy does not meet inclusion criteria
- Men who have received any hormonal manipulation (antiandrogens; LHRH agonist; 5-alpha-reductase inhibitors) within the previous 6 months

4.3 Inclusion of Women and Minorities: All participants will be men without previous treatment for prostate cancer. Men of all ethnic groups and races are eligible for the study. Thus women will not be included in this study.

4.4 Recruitment Plan

Potential research subjects will be identified by a member of the patient's treatment team, the protocol investigator, or research team at H. L. Moffitt Cancer Center. If the investigator is a member of the treatment team, he/she will screen their patient's medical records for suitable research study participants and discuss the study and their potential for enrolling in the research study. Potential subjects contacted by their treating physician will be referred to the investigator/research staff of the study.

The principal investigator may also screen the medical records of patients with whom they do not have a treatment relationship with, for the limited purpose of identifying patients who are eligible to enroll in the study and to record appropriate contact information in order to approach these patients regarding the possibility of enrolling in the study.

During the initial conversation between the investigator/research staff and the patient, the patient may be asked to provide certain health information that is necessary to the recruitment and enrollment process. The investigator/research staff may also review portions of their medical records at H. L. Moffitt Cancer Center in order to further assess eligibility. They will use the information provided by the patient and /or medical record to confirm that the patient is eligible and to contact the patient regarding study enrollment. If the patient turns out to be ineligible for the research study, the research staff will destroy all information collected on the patient during the initial conversation

and medical review, except for any information that must be maintained for screening log purposes.

In most cases, the initial contact with the prospective subject will be conducted either by the treatment team, investigator or the research staff working in consultation with the treatment team. The recruitment process outlined presents no more than minimal risk to the privacy of the patients who are screened and minimal patient health information (PHI) will be maintained as part of a screening log.

5.0 PRE-TREATMENT EVALUATION AND IMAGING

The pre-enrollment clinical evaluation will include a complete medical history, physical examination including digital rectal examination, review of prostate biopsy information including Gleason score, review of any imaging studies, and clinical staging (TNM staging). Patients with up to clinical stage T2a prostate cancer meeting the aforementioned clinical and biopsy criteria are eligible for enrollment. If the patient had their diagnostic biopsy performed at an outside institution, these biopsy slides must be reviewed at our center prior to determining patient eligibility. If there is a discrepancy between the outside and H. L. Moffitt Cancer Center pathology reviews, we will rely on the H. L. Moffitt Cancer Center review to determine eligibility.

Baseline visit: determine patient eligibility. If patient's diagnostic prostate biopsy has not yet been reviewed at pathology, a request will be made to have pathology review the slides and provide a review for diagnosis. Once eligibility is confirmed and patient agrees to participate in the study an informed consent is signed. Pre-mapping imaging and biopsy assessment #1 (week 0 to 12): After the informed consent is signed, the patient will be scheduled for an MRI (DCE and DWI using a 1.5T MRI if possible with a Sentinel Endorectal coil). The regions where both imaging sets indicate the potential for disease will be identified. During the initial transrectal-guided mapping prostate biopsy, all acquired ultrasound images will be registered to the MRI images. Baseline laboratory studies including serum electrolytes, UA, PT/PTT/INR, CBC, electrocardiogram and chest xray will be performed on patients prior to the procedure. A consent (separate from the informed consent to participate in the study) for the biopsy procedure will be obtained per the Cancer Center's policy for any procedure conducted for treatment/diagnosis.

Patients will also be asked to complete an assessment (see appendixes A-D) of urinary, sexual and bowel functioning, as well as overall quality of life, at baseline. These assessments will be completed at the beginning of the study and at 6 months after the RFA procedure during their clinic visit.

6.0 TREATMENT/INTERVENTION PLAN

Before any study procedures are performed (which includes all screening procedures, pre-treatment, treatment/intervention procedures, etc.), all patients will be asked to sign an informed consent form.

Prior to the mapping prostate biopsy, patients will be required to have an EKG and Chest X-Ray. Eligible patients are evaluated with a transrectal-guided transperineal mapping

prostate biopsy. Patients meeting our definition of low-risk or intermediate prostate cancer (up to clinical stage T2a, PSA< 10ng/ml, Gleasons score 6 or 7), will undergo RFA of the regions containing cancer on the mapping biopsy (focal bipolar RFA). Six months following focal bipolar RFA the patient will undergo a second mapping biopsy.

7.0 EVALUATION DURING TREATMENT/INTERVENTION

Before any study procedures are performed (which includes all screening procedures, pre-treatment, treatment/intervention procedures, etc.), all patients will be asked to sign an informed consent form.

Focal bipolar RFA will be done (after 4 weeks and no more than 12 weeks of initial mapping biopsy): a separate informed consent for this procedure will be obtained (which is separate from the informed consent to participate in the study), per the Cancer Center's policy for any procedure conducted for treatment/diagnosis. If the laboratory studies obtained at the pre-mapping biopsy assessment are still valid (within 6 months), they will not be repeated.

Six weeks after focal bipolar RFA; DRE, PSA, assessment of toxicity will be done. Toxicity of transperineal prostate biopsy includes bleeding, infection, urinary retention. Toxicity of focal bipolar RFA includes bleeding, infection, urinary incontinence, urinary retention, erectile dysfunction, urinary urgency, urinary frequency and rectal fistula.

Three months after focal RFA; DRE, PSA, assessment of toxicity will be done as mentioned in the preceding paragraph.

Six months after focal bipolar RFA; DRE, PSA, QOL questionnaire, assessment of toxicity; obtain serum electrolytes, UA, EKG and chest x-ray in preparation for repeat mapping biopsy to be done. The patient will be scheduled for the second MRI imaging and transrectal-guided mapping prostate biopsy # 2 to be completed within 6-8 months after focal bipolar RFA. After a biopsy is requested we will have a patient follow up in 1-2 weeks for discussion of results and assessment of any adverse events (this will be the end of study visit).

Patients will record weekly medical resource utilization data to share with their study coordinator at routine scheduled visits.

8.0 Adverse Event Reporting and Safety Monitoring

The principal investigator will have the primary responsibility for data safety and monitoring. Input will be sought from members of the study protocol concerning data and safety issues. The PI of the study will have primary responsibility for ensuring that the protocol is conducted as approved by the SRC and IRB. The PI will ensure that the monitoring plan is followed, that all data required for oversight of monitoring are accurately reported to the DSMB and/or to the PMC and IRB as required, that all adverse events are reported according to the protocol guidelines, and that any adverse events reflecting patient safety concerns are appropriately reported.

Members of the study team will meet at least monthly. The following data will be reviewed:

1. Rate of accrual
2. Adverse events
3. Protocol deviations and/or violations

Interim analysis is due from the PI once 50% accrual of total patients/subjects has been reached or 10 patients enrolled. The monitor will work directly with the study team to ensure the safety and protocol adherence for each patient. If necessary, corrective action and/or educational programs will occur to ensure subject safety and data integrity. Reports to the SRC, PMC and IRB will be submitted as required.

Biomed Research, Inc. will be performing monitoring services for MCC protocol #17753 on behalf of Trod Medical LLC. Contact information for Biomed below.

8.0 Definitions:

8.0.1 Adverse Event: Any unfavorable and unintended sign, symptom or disease temporally associated with the use of a medical treatment, regardless of whether it is related to the medical treatment.

8.0.2 A serious adverse event (SAE) is defined as any adverse event that results in death, a life-threatening experience, inpatient hospitalization, prolongation of existing hospitalization, persistent disability, or congenital anomaly or birth defect.

8.0.3 Study therapy is the required treatment or procedure defined on the

protocol.

8.0.4 Non-protocol therapy is defined as any treatment or procedure not described in the protocol

8.1 Adverse event assessment:

8.11 The type of event using NCI Common Toxicity Criteria for Adverse Events (CTCAE) version 4.0 will be identified and graded for severity.

8.12 The relationship of the adverse event to the therapy or procedure will be determined as follows: Unrelated; Unlikely; Possible; Probable; Definite

8.13 For reporting purposes, an adverse event is considered unexpected when either the type of event or severity of the event is not listed in the study consent

8.2 Serious Adverse Events (SAEs):

8.2.1 All study-related, unexpected Grade 3 or 4 SAEs will be immediately reported to the IRB. These toxicities will be reviewed by the principal investigator and appropriate measures taken in terms of delaying, modifying or stopping therapy.

8.2.2 The descriptions and grading scales found in the revised NCI Common Terminology Criteria for Adverse Events (CTCAE) version 4.0 will be utilized for adverse event reporting (<http://ctep.cancer.gov/reporting/ctc.html>).

8.2.3 SAEs must be followed until resolution or deemed irreversible.

8.3 Routine reporting:

8.3.1 Serious and/or unexpected adverse events will be reported to the IRB according to current IRB policy as well as Moffitt's Protocol Monitoring Committee (PMC) according to current PMC policy.

8.4 Potential Adverse Events that may occur as part of conducting this study include:

Transperineal prostate biopsy:

- Bleeding
- Infection
- Urinary retention

Focal Bipolar RFA

- Bleeding

- Infection
- Urinary Incontinence
- Urinary Retention
- Erectile Dysfunction
- Urinary Urgency
- Urinary Frequency
- Rectal Fistula

9.0 CRITERIA FOR THERAPEUTIC RESPONSE/OUTCOME ASSESSMENT

The primary endpoint of this study is a negative prostate biopsy in the region that was radio frequency ablated 6 months after treatment.

10.0 CRITERIA FOR REMOVAL/ WITHDRAWAL FROM STUDY

- The study will be terminated if a rectal fistula develops in any patient as a result of treatment.
- The patient may withdraw consent for the study at any time. If at any time the patient develops progressive disease he will be taken off the study and referred for alternative therapy.
- If the participant is not following the study procedures as outlined in the protocol/informed consent, he may be removed from the study. If the participant is removed from the study, he will be referred for alternative therapy.
- If at any time the patient is found to be ineligible for the protocol as designated in the section on Criteria for Patient/Subject Eligibility (i.e., a change in diagnosis, etc.), the patient will be removed from the study.

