The primary endpoint of the trial is assessed at 6 months after focal bipolar RFA by repeat MRI imaging and post treatment mapping biopsy performed the same as pre-treatment. Treatment efficacy, defined as all negative biopsy cores at the site of the focal ablation, will be determined by the results of this mapping biopsy that will include complete biopsy of all regions of the prostate. Secondary endpoints will be evaluated through the standard quality-of-life questionnaires. For those patients not enrolled on this study protocol, their data from completion of the quality-of-life questionnaires will not be included in this investigation. Any adverse events that occur as a result of this study will be recorded and reported to the regulatory committees at Moffitt and IRB.

If after the mapping biopsy the patient does not meet the criteria for focal RFA, he will be excluded from this study protocol but considered and offered other management options for prostate cancer including active surveillance, radical prostatectomy or radiation therapy.

Stopping rules:

Criteria for stopping the Study:

1. If at the second mapping biopsy done at 6 months, more than 4 patients have a positive biopsy in the ablated area, the study will be stopped. This is based on the current treatment failure rate of 20% for radical prostatectomy.
2. If even one patient develops hematuria after the procedure requiring a second procedure to be performed, the study will be terminated.
3. If even one patient requires a Foley catheter for greater than 2 weeks following the procedure, the study will be terminated.
4. If even one patient develops an infection requiring inpatient hospitalization, the study will be terminated.
5. If even one patient develops a rectal fistula the study will be terminated.

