11.2 Sample Size/Accrual Rate

This is a pilot study so the sample size justification is based on providing reasonable precision of the primary efficacy endpoint, the negative biopsy rate at 6 months after focal bipolar RFA. We estimated the negative biopsy rate at 6 months after focal bipolar RFA is greater than or equal to 90%. If the negative biopsy rate at the 6-month visit is 90%, a sample size of 20 patients provides a two-sided 95% confidence interval of 68.3-98.8%. If the negative biopsy rate at the 6-month visit is 95%, the 95% corresponding confidence interval is 75.1-99.9%. Thus, the total sample size for this study will be 20 patients. We estimate an accrual rate of 4 patients a month. We anticipate completion of this study over a one year time period.

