11.4 Analysis of Primary Endpoint

Descriptive statistics will be used to summarize patients' demographic and clinical characteristics collected at each visit. Mean, standard deviation and range will be calculated for continuous variables, and frequency and percentage will be generated for categorical variables. The primary objective is to assess the local oncologic efficacy of focal RFA in men with low-risk prostate cancer. The primary efficacy endpoint is negative biopsy rate at 6 months after focal bipolar RFA. The point estimate and its 95% confidence interval will be calculated using the exact binomial method.

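### Section 10.0 takes treated men with progressive disease off study, but Sections 11.2 and 11.4 set neither the denominator nor a rule for a missing 6-month biopsy, so the primary rate could be overstated

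*Combined protocol and SAP*

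**What the plan says.** Section 9.0 defines the endpoint: "The primary endpoint of this study is a negative prostate biopsy in the region that was radio frequency ablated 6 months after treatment". Section 1.2 likewise reads efficacy from the repeat mapping biopsy. Section 7.0 schedules that biopsy 6 to 8 months after RFA. Before the 6-month work-up, it schedules DRE, PSA and toxicity checks at 6 weeks and 3 months.

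Section 10.0 gives several ways for a treated man to leave before the biopsy:

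- Progression, where removal is mandatory: "If at any time the patient develops progressive disease he will be taken off the study and referred for alternative therapy".
- Withdrawal: "The patient may withdraw consent for the study at any time".
- Non-adherence: "If the participant is not following the study procedures as outlined in the protocol/informed consent, he may be removed from the study".
- Ineligibility discovered later.

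On the analysis, Section 11.4 says: "The point estimate and its 95% confidence interval will be calculated using the exact binomial method". Section 11.2 says: "Thus, the total sample size for this study will be 20 patients".

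**The concern.** Removal for progression is not a random reason for a missing outcome. A man whose cancer advances after ablation may well have residual cancer at the treated site, and he is the man the plan sends elsewhere before the endpoint is measured. If the analysis then uses only men with a biopsy, likely failures leave both numerator and denominator and the negative-biopsy rate rises.

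The plan has no success threshold, so no formal test is affected. The estimate and its interval are the whole primary result. Readers will set them against the assumed rate of at least 90% (Section 11.2) and the 20% failure rate cited for prostatectomy (stopping rule 1, Section 1.2). With no rule fixed beforehand, the denominator could be chosen after the results are known.

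**Working it through.** **1. Is there a rule anywhere?**

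- Section 11.4 names the method but no analysis population.
- Section 11.2 does not say what its 20 counts. The question is real because some consented men never reach treatment. Section 1.2 says: "If after the mapping biopsy the patient does not meet the criteria for focal RFA, he will be excluded from this study protocol". That exclusion applies before RFA, so it does not cover treated men.
- Section 13.1 mentions missing data only as a subject of data-quality reports.
- Section 10.0 does not define progression and does not say whether the 6-month biopsy is still obtained after removal.

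No section scores a treated man without a biopsy.

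**2. Reproduce the plan's figures.** The exact (Clopper-Pearson) interval for x negatives of n runs from the 2.5% quantile of Beta(x, n-x+1) to the 97.5% quantile of Beta(x+1, n-x). For 18/20 this gives 68.3-98.8%, and for 19/20 it gives 75.1-99.9%. Both match Section 11.2.

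**3. Spread across the possible rules.** Assume 20 treated. The number missing (m) and the biopsy results are assumptions, because the documents give neither.

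| Scenario | Biopsied only | Worst case (missing = positive) | Best case (missing = negative) |
|---|---|---|---|
| m = 1, 16 of 19 negative | 16/19 = 84.2% (60.4-96.6) | 16/20 = 80.0% (56.3-94.3) | 17/20 = 85.0% (62.1-96.8) |
| m = 2, 16 of 18 negative | 16/18 = 88.9% (65.3-98.6) | 16/20 = 80.0% (56.3-94.3) | 18/20 = 90.0% (68.3-98.8) |

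The bounds lie 1/20 = 5 points apart for each missing biopsy. With none missing, all the rules agree.

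**4. Direction of the bias.** Let p be the positive rate in biopsied men and q the assumed chance that a missing man is positive at the ablated site. The biopsied-only rate minus the expected all-treated rate is (m/20) × (q - p).

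| q | m = 1, p = 3/19 = 15.8% | m = 2, p = 2/18 = 11.1% |
|---|---|---|
| 0 | -0.8 points | -1.1 points |
| q = p | 0 | 0 |
| 50% | +1.7 | +3.9 |
| 100% | +4.2 | +8.9 |

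The rate is inflated only when q exceeds p. Below p the sign reverses.

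**5. Error of the opposite convention.** Counting every missing man as not negative gives an error of -(m/20) × (1 - q). At q = 50% this is -(1/20) × 0.5 = -2.5 points for one missing and -(2/20) × 0.5 = -5.0 for two. It exceeds the biopsied-only error in size whenever q < (1 + p)/2, which is 57.9% for 16/19 and 55.6% for 16/18.

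**The case against.** **The plan is silent rather than wrong.** A reader might infer that it prescribes a biopsied-only analysis. It does not: Section 10.0 takes men off the study and says nothing about removing them from the analysis. Section 11.2 computes its intervals with 20 as the denominator, which hints at 20 men with outcomes. That is fair, but a hint does not say how an unbiopsied man among the 20 would be scored.

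**Few men will be affected, and progression need not be local.** The background section describes slow-growing disease, and only two checks are scheduled before the 6-month work-up. A man whose progression is found at the 6-month biopsy already has his endpoint. Progression could also lie outside the ablated area. All of this stands. It limits the likely size and makes the direction conditional, but it does not supply the missing rule.

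**Scoring all missing men as failures can do more harm than omitting them.** Step 5 shows this for q below about 56-58%. Applied to men missing for unrelated reasons, it also turns a local endpoint into a composite. This stands too, and it is why the fix confines that scoring to removal for progression and labels it a convention.

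**Conclusion.** The point holds in conditional form. It is certain that the plan mandates removal for progression and gives neither a denominator nor a missing-biopsy rule. Upward bias follows only if such men are left out and are positive at the ablated site more often than biopsied men. That is plausible for removal because of progression, but the documents do not establish it. Under the assumed two-missing case, the same data can be reported as anything from 80.0% to 90.0%, with widely overlapping intervals. The values of m and q are assumptions throughout.

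A reader might also infer that Section 10.0 conflicts with stopping rule 1 in Section 1.2. The documents do not support that. The rule is met when, at the second mapping biopsy, "more than 4 patients have a positive biopsy in the ablated area". A man without that biopsy is simply not counted, and the two sections are consistent.

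**What to change.** - **Sections 11.2 and 11.4:** define the primary denominator as all men who received RFA, and say whether the planned 20 are enrolled, treated or biopsied.
- **Section 10.0:** state that leaving protocol follow-up, for whatever reason, does not remove a treated man from the analysis.
- **Primary rate:** count men removed for progression before the 6-month biopsy as not negative. Declare this as a conservative convention, because progression may lie outside the ablated site.
- **Biopsies missing for other reasons:** fix one scoring rule in advance.
- **Reporting, whichever rule is chosen:** give the biopsied-only rate and the best-case and worst-case bounds, each with its exact 95% interval, plus the number of missing biopsies and the reason for each.
- **Definition:** the protocol team should state what counts as progressive disease. No clinical rule is proposed here.

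The cost is a few sentences and no added procedures. The reported rate may be slightly lower and may understate local control. The biopsied-only rate and the best-case bound let the reader see by how much.
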